***Addiction Dimensions for Assessment and Personalised Treatment** (ADAPT [53]). The ADAPT is a clinician completed 14-item instrument used for drug addiction treatment planning and outcome evaluation with three-subscales: opioid addiction severity, coexisting health and social problems, and recovery strengths.

***Clinical Global Impression** (CGI-S and I; [36]). The CGI is a single item clinician assessment of disorder severity and improvement.

Craving Experience Questionnaire (CEQ-F [frequency] [56]). The CEQ-F will be completed for opioids (CEQ-F[H] and cocaine (CEQ-F[C]). This scale has a 14-day recall period and captures intensity, imagery, and intrusiveness aspects of drug craving.

Visual analogue scale of maximum need (VAS-N[H/C] and want (VAS-W[H/C]). These single item (0-100) rating scales have a recall period of the past 14 days.

Difficulties in Emotion Regulation Scale – Short Form (DERS-SF; [37]). The DERS The DERS is an 18 item self-report scale which records current emotional dysregulation in six subscales: non-acceptance, goals, impulse, aware, strategies and clarity.

QIDS-SR ([39]) The QIDS-SR is a brief scale which assesses the frequency of depressive symptoms during in past two weeks.

Work and Social Adjustment Scale (WSAS; [38]). The WSAS is a 5-item scale which records the extent of social functioning impairment perceived to be caused by OUD in the past two weeks.

Service User Recovery Evaluation (SURE; [6]). The SURE is a patient-reported outcome measure and is a multi-dimensional measure of perceived recovery status.

Patient reported outcome measure - Status (PRO-S and I). The PRO-S is a single 7-point item assessment of the extent to which the participant perceives the severity of their opioid-related problems at baseline and at follow-up.

EQ-5D-5L ([39])The EQ-5D-5L is a brief generic scale which captures health status on five dimensions: mobility, self-care, usual activities, pain/discomfort, anxiety/depression, and with a 20cm vertical visual analogue scale. These responses generate health profiles from which health utilities can be calculated for economic evaluations.

Alcohol and Drug Service Use Schedule (ADSUS). The ADSUS is a well-developed structured patient interview that records use of health, social, welfare and criminal justice services and crime. The ADSUS was successfully used in the ARC trial.

Keyworker Contact Form (KCF). The KCF records the clinical team's direct and indirect time working on EXPO.

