- **Measure 1;** Total retention time - Days enrolled in maintenance medication for opioid use disorder (OUD) from first day following grace period (day 8) to day 168 (across 161 days weeks 2 to 24)
- **Measure 2;** Survival time - Days from randomisation to first discontinuation (i.e. time (days) enrolled in study treatment).
- ***Measure 3;** Time (days) enrolled in study treatment (retention) from week 24 to date last participant randomised plus 9 months.

*Measure 3 Will be analysed as part of the extended phase of the study and detailed in a separate SAP

Objective 4 OUD and CUD remission status

- Assessed by Standard Clinical interview for Dependence - research version (SCID-RV)
 - Remission status (Yes/No) at 12 weeks
 - Remission status (Yes/No) at 24 weeks

Objective 5 Clinician rated impression of patient response to treatment (at 24 weeks)

- **Measure 1;** Clinical Global Impression scale (severity and improvement - CQI-S/CGI-I)
- **Measure 2;** Addiction Dimensions for Assessment and Personalised Treatment (ADAPT)

Objective 6 Patient reported recovery outcomes (at 24 weeks)

Measure 1; Craving response using Craving experience questionnaire (CEQ-F)

Measure 2; Visual analogue craving rating (Need) (VAS-N)

Measure 3; Visual analogue craving rating (Want) (VAS-W)

Measure 4; Social functioning using Work and Social Adjustment Scale (WSAS)

Measure 5; Depression using Quick inventory of Depressive Symptomatology (QIDS-SR)

Measure 6; Improvement and Recovery using Substance Use Recovery Elevator (SURE)

Measure 7; Patient Reported Outcome Status (severity and improvement - PRO-S/PRO-I)

Measure 8; Emotion regulation using Difficulties in Emotion Regulation Scale short form (DERS-SF)

Measure 9; Alcohol quantity, frequency, maximum consumption (ALC-QFM (TOP) - quantity and frequency only - maximum will be reported descriptively).

Objective 7 Mediation analysis

Mediation of craving, work and social adjustment, and cognitive function on outcome.

Mediator measures;

- Visual analogue scale (VAS) for the perceived need and want for non-medical opioids and cocaine (VAS-N and VAS-W)
- Craving Experience questionnaire, frequency version (Heroin) (CEQ-F-H)
- Quick Inventory of Depressive Symptomatology – Self-Report (QIDS-SR)
- Montreal Cognitive Assessment (MoCA)
- Work and Social Adjustment Scale (WSAS)

Moderator measures;

- Sex at birth

- Age
- Current injecting status
- Centre
- Measure/Outcome baseline

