Appendix 2 details the outcome measures to be analysed and their associated models.

A causal mediation analysis (including craving, MoCa, QUIDS-SR and WSAS as mediators in separate models) will be implemented using a counterfactual framework to include a treatment/mediator interaction and covariates, based on univariable path screening, and with bias corrected bootstrapped estimates.

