Used for substance use disorders (SUD) clinicians to obtain a brief multi dimension patient profile of addiction related severity, health and social problem complexity and recovery strengths	A 14 item measure consisting of three subscales. Each subscale total is calculated by summing the individual items in the subscale. An overall measure total score is not obtainable, just 3 subscale scores.	Items 1, 3, 4, 5, 9, 10 rated; 0 'None' and 1 'Present' Items 2, 5, 6, 7, 8, 11, 12, 13, 14 rated 0 'None', 1 'Low', 2 'Moderate' and 3 'High'.	1. Addiction severity (items 1 – 3). 2. Coexisting problem complexity (items 4 – 10). 3. Recovery Strengths (items 11 – 14)	1. Higher scores indicate worse 2. Higher scores indicate better 3. Higher scores indicate better	None found None found None found	1. Low 0 – 1, moderate 2 – 3 and high 5 – 4 2. Low 0 – 2, moderate 3 – 5 and high 6 – 15 3. Low 0 – 5, moderate 6 – 8 and high 9 – 11
Craving response using Craving experience questionnaire (CEQ-F)						
No reference available; below scoring derived from MACRO database						
Craving Questionnaire						
Craving Experience	11 item scale.	Each item rated on a scale from 0 – 10.	None identified	Higher scores indicate more severe craving	None found	None found
Total scale calculated by summing the 11 items, therefore final score ranges from 0 to 110.						
Visual analogue craving rating (Need/Want) (VAS-N/VAS-W)						
No reference available; below scoring derived from MACRO database						
Self-report craving rating	Two individual items one measures rating need and the other rating want.	Both items are scored on a 0 – 100 continuous scale	None identified	Higher scores indicate more severe craving	None found	None found
Total score is not to be calculated from the two scales. However, the two scale scores will range from 0 to 100.						
Social functioning using Work and Social Adjustment Scale (WSAS)						
Mundt, J C., et al., The Work and Social Adjustment Scale: a simple measure of impairment in functioning (2002). British Journal of Psychiatry , 180, 461 – 464.						

Self-report scale of functional impairment attributable to an identified problem.	Five item scale. Total score calculated by summing up 5 items in the scale.	Items rated on a 0 to 8 scale with 0 indicating no impairment and 8 indicating very severe impairment	None identified	Higher scores indicate better state.	None found	None found

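### SAP Appendix 3 labels a higher WSAS total as better, but the row's own coding and sum make a higher total worse; correct the label so that benefit and harm are not swapped in the write-up

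*SAP*

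**What the plan says.** The WSAS row of SAP Appendix 3 contains four statements that matter here.

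- Definition: "Self-report scale of functional impairment attributable to an identified problem".
- Scoring: "Total score calculated by summing up 5 items in the scale".
- Item coding: "Items rated on a 0 to 8 scale with 0 indicating no impairment and 8 indicating very severe impairment".
- Direction: "Higher scores indicate better state".

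The subscale, missing-value and threshold cells hold no rule for WSAS. Protocol Section 9.1 describes the same construct: the scale "records the extent of social functioning impairment perceived to be caused by OUD in the past two weeks".

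WSAS has two roles in the analysis. It is Measure 4 under secondary Objective 6 at 24 weeks (SAP Section 5.2), analysed with a GLM that adjusts for the baseline score and the stratification factors (Section 6.7). Appendix 2 sends the reader to Appendix 3 for its scoring. It is also one of the mediators in the causal mediation analysis (Sections 5.2 and 6.7).

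**The concern.** The definition, item coding and sum all say that a high WSAS total means more impairment. The Direction cell says that a high total is the better state. Both cannot be true of the same total, and nothing elsewhere in the SAP or protocol corrects the label.

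The Direction column is where a reader of the table learns which sign of a treatment difference is favourable. Someone drafting a results table, a footnote or the text on social functioning could take it at face value. A lower mean under BUP-XR, which is less impairment, would then be described as a disadvantage, and a higher mean as an advantage. If the conflict is noticed only at the analysis stage, the SAP does not say whether the coding or the label governs. That choice would then be made after data lock, possibly with results in view.

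**Working it through.** The plan states no range for the WSAS total, so there is no figure to reproduce. The check is arithmetic on the SAP's own rule.

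**1. Range.** The inputs, all from the Appendix 3 row, are five items, each 0 to 8, and a plain sum.
- Minimum: 5 × 0 = 0, no impairment on any item.
- Maximum: 5 × 8 = 40, very severe impairment on every item.

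**2. Direction.** Total = x1 + x2 + x3 + x4 + x5. Raising any item by one point moves it towards very severe impairment and raises the total by 1. A check over a grid of item values found no exception. Higher is therefore worse.

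**3. What the label would do to a result.** Assume, for illustration only, week-24 means of 12 under BUP-XR and 16 under MET/BUP-SL.
- As scored in the SAP: 12 − 16 = −4, which is less impairment under BUP-XR and so a benefit.
- Read through the Direction cell: −4 is a move away from the better state, and so harm.
- On a reversed total: (40 − 12) − (40 − 16) = 28 − 24 = +4. The label fits only this version, and the SAP does not specify it.

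**4. Does the estimate change?** A label alone changes no data. Even an actual reversal of both visits would only mirror the result. Write the GLM as Y24 = a + bT + cY0 + other terms, where T is treatment and Y0 is baseline. With R = 40 − Y at both visits:

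R24 = (40 − a − 40c) − bT + cR0 − other terms.

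The treatment coefficient goes from b to −b, the confidence limits change sign and swap places, and the p-value is the same.

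**5. Does the mediated effect change?** Again a label changes no data. Suppose that the mediator M really were recoded to M′ = 40 − M. With a treatment-by-mediator interaction, as in Section 6.7, the linear predictor is

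b0 + b1T + b2M + b3TM = (b0 + 40b2) + (b1 + 40b3)T − b2M′ − b3TM′.

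Every participant keeps the same predicted outcome. The treatment-to-mediator path and the mediator-to-outcome path each change sign, and the two changes cancel. The natural direct and indirect effects on days abstinent are unchanged. Only the words attached to the separate paths (functioning improved or worsened) depend on the direction.

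**6. Is a reversal implied?** Other rows of Appendix 3 suggest not.

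| Measure | What the row states |
|---|---|
| DERS-SF | Reverse coding of the awareness scale is written out |
| SURE | Re-weighting of items is written out, so that a higher total is better |
| CEQ-F | Plain sum; higher is labelled more severe craving |
| QIDS-SR | Higher is labelled worse |
| WSAS | Plain sum of impairment items, no reversal; higher is labelled better |

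Where the authors wanted recoding they said so, and the other severity totals carry the expected label.

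**The case against.** The strongest reply is that this is a slip in a descriptive cell with no effect on any planned computation. That is largely right. The items, total, baseline covariate and model are the same whatever the cell says. WSAS has no threshold or responder rule that uses direction, and neither the item-mean substitution nor the use of baseline WSAS as a candidate predictor of missingness (Section 4.6) depends on it. A careful writer would also see the neighbouring cells, which speak of impairment, and would probably interpret the result correctly. Section 5.2 says only that Appendix 3 holds scoring details; it does not tell anyone to interpret effects from the Direction column. Finally, WSAS is one of nine Objective 6 measures, and Section 4.3 calls all secondary analyses exploratory.

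These arguments limit the consequence but do not remove the contradiction. The row has seven cells for seven column headings, and the phrase sits in the Direction position, so it is not an artefact of text extraction. The SAP's revision history mentions adjustments to WSAS scoring, but that does not settle the matter, because the current row still disagrees with itself.

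A reader might infer that the SAP scores WSAS backwards. It does not: the coding and the sum agree with each other and with the construct. A reader might also infer that the mediation conclusion would reverse. Step 5 shows that it would not.

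**Conclusion.** The point holds as a labelling error. On the SAP's own coding and sum, a higher WSAS total (0 to 40) means worse functioning, and the Direction cell states the opposite. This rests on the Appendix 3 row alone, read as written, with no reversal step because none is stated.

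No numerical result changes: the estimate, confidence interval and p-value of the week-24 secondary analysis stand, and so does the indirect effect in the mediation analysis. What is at risk is interpretation. If the label is followed, the treatment difference on WSAS could be reported with benefit and harm exchanged, and the WSAS pathway could be described the wrong way round. That outcome is conditional on someone using the label; the documents do not show that it would happen. The primary outcome is unaffected. The correction should be made before analysis because it is certain and nearly free, but it does not threaten the trial's main conclusion.

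**What to change.** Change the WSAS Direction cell in SAP Appendix 3 to say that higher scores indicate worse functioning, and add the range 0 to 40. If a reversed total was in fact intended, state it in the Scoring cell as 40 minus the sum, apply it at baseline and at follow-up, and keep the present label.

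Whichever is chosen, use the same direction when interpreting and labelling the week-24 secondary result, the table footnotes and the mediation pathways, and check variable labels in the analysis syntax for the old wording. While the table is open, the ADAPT row deserves the same look, since coexisting problem complexity is also labelled as better when higher; that row was not worked through here.

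The cost is one cell and a short consistency check. No data, model or sample size changes.

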APPENDIX 4 – ASSUMPTIONS OF MODELS

Assumption	Checking
Poisson Regression	
distribution of counts (conditional on the model) follow a Poisson distribution	calculate the expected counts and plot these with the observed counts to see if they are similar
The mean and variance of the model are identical	Graphical display Pearson dispersion statistic
If you satisfy this assumption you have equidispersion. often this is not the case and your data are either under- or over dispersed.	See appendix 1 for more detail.
Generalised Linear mixed model	
Linearity the relationship between the independent and dependent variables to be linear	scatter plots of the model residuals vs predictor
U8Residuals/errors are independent Little or no autocorrelation in the data. (residuals should be independent from each other)	Scatter plot Durbin-Watson test
Residuals/Errors are normally distributed	Q-Q-Plot
Residuals/Errors have constant variance	Scatter plot of standardized residuals versus predicted values
There should be no homoscedasticity of error terms	
No or little multi-collinearity (independent variables should not be highly correlated with each other)	inspection of correlation coefficients and Tolerance/VIF values
ORDINAL LOGISTIC REGRESSION	
There should be no multi-collinearity	inspection of correlation coefficients and Tolerance/VIF values
You should have proportional odds	full likelihood ratio test comparing the fit of the proportional odds model to a model with varying location parameters
BINARY LOGISTIC REGRESSION	
Linear relationship between the continuous independent variables and the logit transformation of the dependent variable.	Box-Tidwell (1962) procedure
Your data must not show multi-collinearity	inspection of correlation coefficients and Tolerance/VIF values
There should be no significant outliers, high leverage points or highly influential points	Box plots
Cox regression model	
proportional hazards the ratio of the hazards for any two individuals is constant over time	Kaplan Meier curves
linear covariate relationships	residual plots
The Cox model assumes that each variable makes a linear contribution to the model
